#### **4.4.2 Secondary Efficacy Endpoints**

##### **4.4.2.1 Secondary Efficacy Variable 1**

The Secondary Efficacy Endpoint 1 will be mean VITA shade score at 12 weeks after tooth bleaching and the comparison of Test Dentifrice to the Reference Dentifrice.

###### **4.4.2.1.1 Statistical Hypothesis, Model and Method of Analysis**

Study product differences will be tested under same hypothesis stated in [Section 4.4.1.2](#). Mean VITA Bleached guide shade will be analyzed using a repeated measures ANOVA model with treatment group and study time points (Visit 2 to 5) as factor and treatment group by time point (Visit 2 to 5) as interaction. Subject will be included as a repeated measure with unstructured covariance matrix; the Kenward Rogers degrees of freedom approach will be applied (Kenward and Roger, 1997). If the model with unstructured covariance matrix does not converge then compound symmetry covariance matrix will be used.

Refer to [Section 4.4.1.2](#). Mean differences between Test Dentifrice compared to Reference Dentifrice in Mean VITA shade score at 12 weeks after tooth bleaching will be presented along with 95% CIs and p-values in Table 14.2.2.2.1. All p-values presented will be two-sided and assessed at the 5% significance level.

The assumption of normality and homogeneity of variance in repeated measures ANOVA will be investigated. In case of violation of these assumptions, a suitable nonparametric test (Van Elteren Test adjusted for randomization stratification) will be performed to assess comparisons (Test Dentifrice vs. Reference Dentifrice at Week 12) and the results will be provided to support

the repeated measures ANOVA results. The non-parametric results will be considered confirmatory under the observation of strong violations of the assumptions.

#### **4.4.2.2 Secondary Efficacy Variable 2**

For comparison of extrinsic dental after stain the Secondary Efficacy Endpoint 2 will be mean scores at 12 and 24 weeks after tooth bleaching in:

- Total MLSI (Area (A) x Intensity (I))
- MLSI (AxI) for gingival sites (AxI)
- MLSI (AxI) for interproximal sites (AxI)
- MLSI (AxI) for body sites (AxI)
- Total MLSI Area (A)
- Total MLSI Intensity (I)

Extrinsic dental stain will be assessed on the facial surfaces of the 6 maxillary anterior teeth (6-11) [Universal tooth numbering system] at Visits 1-5), using (MLSI) described in section 9.2.2 of the study Protocol (v2.0, dated 13-Nov-2023).

##### **4.4.2.2.1 Statistical Hypothesis, Model and Method of Analysis**

The results for mean total MLSI Area x Intensity (AxI), mean total MLSI (AxI) for gingival sites (AxI), mean total MLSI (AxI) for interproximal sites (AxI), mean total MLSI (AxI) for body sites (AxI), mean total MLSI Area (A), and mean total MLSI Intensity (I) will be obtained from the Repeated Measures ANOVA detailed in Section 4.4.1.2. Mean differences between Test Dentifrice compared to the Reference Dentifrice in mean Total MLSI (A×I) score at 12 and 24 weeks after tooth bleaching will be presented along with 95% CIs and p-values in Table 14.2.3.2 for all subjects in the mITT population. Significance testing will be conducted at the two-sided 5% significance level. Study product differences for each of the aforementioned efficacy variables will be tested under the null hypotheses described below at 12 and 24 Weeks:

- **Total MLSI (Area (A) x Intensity (I))**

H0: there is no difference in mean total MLSI Area x Intensity (A×I) scores between Test Dentifrice and Reference Dentifrice;

H1: there is a difference in mean total MLSI Area x Intensity (A×I) scores between Test Dentifrice and Reference Dentifrice;

Descriptive statistics (n, mean, SD, Standard Error [SE], median, minimum, and maximum) will be presented for Mean Total MLSI (AxI) score at each assessment time point in Table 14.2.3.1 for all subjects in mITT Population by study product. Raw mean  $\pm$  (SE) of mean Total MLSI (AxI) score at each timepoint will be plotted by study product in Figure 14.2.2.1 for all subjects in the mITT population.

- **Gingival sites (AxI)**

H0: there is no difference in mean MLSI (AxI) scores for gingival sites between Test Dentifrice and Reference Dentifrice;

H1: there is a difference in mean MLSI (AxI) scores for gingival sites between Test Dentifrice and Reference Dentifrice;

- **Interproximal sites (AxI)**

H0: there is no difference in mean MLSI (AxI) scores for interproximal sites between Test Dentifrice and Reference Dentifrice;

H1: there is a difference in mean MLSI (AxI) scores for interproximal sites between Test Dentifrice and Reference Dentifrice;

- **Body sites (AxI)**

H0: there is no difference in mean MLSI (AxI) scores for body sites between Test Dentifrice and Reference Dentifrice;

H1: there is a difference in mean MLSI (AxI) scores for body sites between Test Dentifrice and Reference Dentifrice;

- **MLSI (A)**

H0: there is no difference in mean total MLSI Area (A) scores between Test Dentifrice and Reference Dentifrice;

H1: there is a difference in mean total MLSI Area (A) scores between Test Dentifrice and Reference Dentifrice;

- **MLSI (I)**

H0: there is no difference in mean total MLSI Intensity (I) scores between Test Dentifrice and Reference Dentifrice;

H1: there is a difference in mean total MLSI Intensity (I) scores between Test Dentifrice and Reference Dentifrice;

Descriptive statistics (n, mean, SD, Standard Error [SE], median, minimum, and maximum) will be presented for all the aforementioned efficacy variables at each assessment time point in Table 14.2.3.1 for all subjects in mITT Population by study product. Raw mean  $\pm$  (SE) of mean Total MLSI (AxI) score at each time point will be plotted by study product in Figure 14.2.2.1 for all subjects in the mITT population.

Individual and derived MLSI (AxI) score data will be listed for each subject by visit and study product group in Listing 16.2.6.2.1 and Listing 16.2.6.2.2 respectively for all randomized subjects.

The assumption of normality and homogeneity of variance in the repeated measures ANOVA model will be investigated. In case of violation of these assumptions, a suitable nonparametric test (the Van Elteren test, adjusted for the randomization stratification) will be performed for each comparison at week 12 and 24 and results will be provided to support the repeated measures ANOVA results.

#### **4.4.3 Exploratory Efficacy Variables**

There will be no adjustment for multiplicity in the analyses for exploratory efficacy variables.

##### **4.4.3.1 Exploratory Efficacy Variable 1**

The Exploratory Endpoint 1 will be Mean sensitivity questionnaire scores pre and post bleaching to access tooth sensitivity of subjects and comparison between Test Dentifrice and Reference Dentifrice. To assess tooth sensitivity below questionnaire will be used:

- Visual Analogue Scale (VAS)
- Labelled Magnitude Scale (Intensity, Duration, Tolerability, Description) - LMS
- Bothersomeness Score (NRS)

Descriptive statistics (n, missing, mean, SD, standard error [SE], median, minimum, and maximum) will be presented for VAS score, NRS Score and LMS (Intensity, Duration, Tolerability, Description) score at each assessment time point in Table 14.2.4.1 for all subjects in the mITT population by study product within Strata.

Additionally, number of subjects who experienced tooth sensitivity will be summarized by study product group and stratum [DH (Y/N)] in Table 14.2.4.1.

Individual data for VAS score, LMS score and NRS score will be listed for each subject by study product group and visit in Listing 16.2.6.3 for all randomized subjects.

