### 9.2.3 Tooth Sensitivity Questionnaire

The tooth sensitivity questionnaire ([see Appendix 15.4](#)) will be completed by the subject at the study site at Visits 1-3, to evaluate the overall tooth sensitivity experienced by the subject over the previous week. Thus, the questionnaire should record the subject’s overall experience of the preceding 7 days. The questionnaire will be completed at the study site without reference to other subjects and will be checked for completeness prior to the subject leaving the site. Study personnel should demonstrate to subjects the correct completion of this questionnaire prior to administering.

Subjects will indicate whether they have felt tooth sensitivity during the previous week. Those who indicate they have not felt tooth sensitivity will not be required to complete the rest of the questionnaire. Subjects who indicate they did feel tooth sensitivity will complete the remainder of the questionnaire comprising the VAS, LMS and Bothersomeness numerical rating scale (NRS).

Subjects will rate their overall tooth sensitivity using a 100mm VAS with end anchors of ‘No Sensitivity’ to ‘Extreme Sensitivity’.

The LMS apply psychophysical procedures (magnitude estimation and cross-modality magnitude matching) to condition specific descriptive words relevant to the subject’s response ([Gracely et al., 1978](#)). The descriptive words are then aligned along a Visual Analogue Scale (VAS) at distances that reflect the psychological distances between words. These scales have been piloted and validated in a previously reported dentine hypersensitivity trials ([Heaton et al.,](#)

2013, [Mason et al., 2019](#)). The LMS will be used to rate the intensity, duration, tolerability and descriptive quality of their tooth sensitivity using the four individual 100 millimetre (mm) LMS.

The study staff will measure the line segment marked-off in mm from bottom to top along the line (for LMS) and from left to right (for the VAS) and record this in the eCRF.

The subject will also complete a NRS for bothersomeness for which the subject should circle an appropriate number on the scale.

All questionnaire data shall be recorded in the CRF upon return of completed questionnaire.

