### 12.3.3 Exploratory Analysis

#### ***Tooth sensitivity questionnaire***

For the exploratory endpoints listed below, the mean scores of the responses to the sensitivity questionnaire scores will be summarized for each time point; screening (Visit 1), prior to the start of tooth bleaching (Visit 2) and at the completion of tooth bleaching (Visit 3) and analyzed.

- Visual analogue scale
- Labelled Magnitude scales
- Bothersomeness score

These analyses will be performed for the mITT population and by strata group (clinically diagnosed DH (Y/N) (where applicable) at screening.

Additionally, the following data from the questionnaires will be presented with summary statistics.

- Number of subjects who experienced tooth sensitivity by treatment group and stratum (Clinically-diagnosed DH [Y/N])

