### ***Change in VITA shade from pre-to post to bleaching***

The mean Vita shade will be summarized for prior to the start of tooth bleaching (Visit 2) and at the completion of tooth bleaching (Visit 3) and analyzed. An Analysis of Covariance (ANCOVA) model will be applied to analyze the Change from pre-to-post bleaching treatment in the mean VITA-Shade color score with study product as a fixed effect and the mean VITA-Shade color score prior to the start of tooth bleaching fitted as a covariate. The least square means for each study product will be presented along with the pairwise differences.

The assumption of normality and homogeneity of variance will be investigated. In case of violation of these assumptions, a suitable non-parametric test will be performed, and results will be provided to support the parametric results.

Additional details of the proposed statistical analysis of the exploratory endpoints will be documented in the statistical analysis plan (SAP).

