**Table 1-1 Study Objectives and Endpoints**

Objectives	Endpoints
Primary Objective	Primary Endpoint
To compare tooth color after 24 weeks twice daily use of a '5% KNO 3 /1% alumina/5% STP' dentifrice compared to a regular fluoride dentifrice following peroxide tooth bleaching as measured by VITA Bleached guide 3D-Master.	Mean VITA shade score at 24 weeks after tooth bleaching.
Secondary Objectives	Secondary Endpoints
To compare tooth color after 12 weeks twice daily use of a '5% KNO 3 /1% alumina/5% STP' dentifrice compared to a regular fluoride dentifrice following peroxide tooth bleaching as measured by VITA Bleached guide 3D-Master.	Mean VITA shade score at 12 weeks after tooth bleaching.
To compare extrinsic dental stain after 12 and 24 weeks, twice daily use of a '5% KNO 3 /1% alumina/5% STP' dentifrice compared to a regular fluoride dentifrice following peroxide tooth bleaching as measured by Modified Lobene Stain Index.	Mean MLSI at 12 and 24 weeks after tooth bleaching in: 

• Total MLSI (Area (A) x Intensity (I))

• Gingival sites (AI)

• Interproximal sites (AI)

• Body sites (AI)

• MLSI (A)

• MLSI (I)

Exploratory Objectives	Exploratory Endpoints
To compare subject-perceived tooth sensitivity during peroxide tooth bleaching with twice daily use of a '5% KNO 3 /1% alumina/5% STP' dentifrice compared to a regular fluoride dentifrice, as measured by subject-completed sensitivity questionnaire overall and within strata (clinically-diagnosed DH [Y/N])	Mean sensitivity questionnaire scores pre and post peroxide tooth bleaching in: 

• Visual analogue scale (VAS)

• Labelled Magnitude scales (Intensity, Duration, Tolerability, Description) –

• Bothersomeness score -NRS

To explore subject's experience of peroxide tooth bleaching when simultaneously using either a '5% KNO 3 /1% alumina/5% STP' dentifrice or a regular fluoride dentifrice.	Post-whitening questionnaire
To confirm the tooth whitening efficacy of peroxide tooth bleaching with concurrent, twice daily use of '5% KNO 3 /1% alumina/5% STP' dentifrice and a regular fluoride dentifrice as measured by VITA Bleached guide 3D Master.	Change in mean VITA shade score from pre to post tooth bleaching
Safety	

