## **5 Changes to the Protocol Defined Statistical Analysis Plan**

There were no changes or deviations to the originally planned statistical analysis specified in the protocol amendment (Dated: 13-Nov-2023).

<Compound/Product>

<Protocol Number>

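### The SAP gives no between-product estimate for the sensitivity scores the protocol says will be analyzed, and no rule for scoring subjects who report no sensitivity

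*SAP*

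**What the plan says.** The objectives tables of both documents (Protocol Table 3-1, SAP Table 1-1) contain the exploratory objective "To compare subject-perceived tooth sensitivity during peroxide tooth bleaching" between the two products. The comparison is to be made in the whole group and by DH stratum.

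Protocol 12.3.3 says the VAS, LMS and bothersomeness scores will be summarized at Visit 1, Visit 2 and "at the completion of tooth bleaching (Visit 3) and analyzed". On the level of analysis it adds: "These analyses will be performed for the mITT population and by strata group". It leaves the detail for exploratory endpoints to the SAP.

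SAP 4.4.3.1 names a comparison of Test with Reference as part of the endpoint. It then plans descriptive statistics "for all subjects in the mITT population by study product within Strata", plus the number of subjects with sensitivity by product and stratum. SAP section 5 states: "There were no changes or deviations to the originally planned statistical analysis specified in the protocol amendment".

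On data collection, Protocol 9.2.3 says of the questionnaire: "Those who indicate they have not felt tooth sensitivity will not be required to complete the rest of the questionnaire". SAP 4.4.4 rules out imputation of missing data.

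**The concern.** There are two linked gaps.

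First, an objective to compare needs a stated contrast. If the SAP is followed as written, no between-product difference or interval is pre-specified for any sensitivity score, and nothing in its text provides for a result over both strata. Any comparison in the report would then be informal or devised after unblinding.

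Second, the means themselves may not compare randomised groups. A subject with no sensitivity supplies no VAS, LMS or NRS value, and the SAP does not say what value, if any, is assigned. If none is, each Visit 2 and Visit 3 mean covers only subjects who reported sensitivity after product use began. If the test dentifrice prevented mild sensitivity, its remaining sensitive subjects would be the more severe ones, and its mean could look worse because the product worked.

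This matters beyond tidiness. Protocol Section 2 describes the existing evidence on potassium dentifrices during bleaching as hard to interpret, and Section 2.1 says the trial will explore that question.

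**Working it through.** **1. Is a between-product analysis specified anywhere?** SAP text and display list (Appendix 1), side by side:

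| Endpoint | Method in SAP text | Statistical-analysis table | SAS raw output |
|---|---|---|---|
| Mean VITA shade | Repeated measures ANOVA, difference, 95% CI | 14.2.2.2.1 | 16.1.9.1.1 |
| MLSI | Same model | 14.2.3.2 | 16.1.9.2 |
| VITA change over bleaching (exploratory) | ANCOVA, difference, 95% CI | 14.2.4.4 | 16.1.9.3 |
| Sensitivity scores (exploratory) | Descriptive, by product within strata | None (summary 14.2.4.1 only) | None |

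Exploratory status does not explain the gap, because the VITA change endpoint is also exploratory and is modelled. Protocol 12.3.3 uses the same pairing, summarized and then analyzed, for that endpoint and follows it with an ANCOVA. For the post-whitening questionnaire it promises summary statistics only. The difference in wording appears deliberate.

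**2. What happens to a No answer?** The form (Protocol 15.3) tells the subject to stop after a No. Neither document assigns a score to that answer, and SAP 4.4.4 imputes nothing. The most natural programming result is a blank, which drops out of the mean. The planned n, missing count and number of sensitive subjects would reveal this selection but not correct it.

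**3. How many subjects?** The documents give no figure for this endpoint. Their sample size concerns VITA shade (Protocol 12.1: difference 1, SD 2, 80% power) and reproduces at two-sided 5%:

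- n per arm = 2 × (1.96 + 0.8416)² × 2² / 1² = 62.8, so 63. The t-test version gives 63.8, so 64.
- 128 / (1 − 0.20) = 160 randomized, 80 per arm.

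The 64 is the 24-week completer count. The questionnaire ends at Visit 3, which is 14 + 7 = 21 days after randomisation. One post-bleaching color assessment, which Visit 3 supplies, is enough for mITT. Early dropout is not given, so the Visit 3 number per arm lies between 64 (all assumed dropout occurs early) and 80 (none does). With DH at 30–50% (Protocol 5.4) and 1:1 allocation within stratum:

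| Per arm | From 64 | From 80 | Range |
|---|---|---|---|
| Overall | 64 | 80 | 64–80 |
| DH | 64 × 0.30 = 19.2 to 64 × 0.50 = 32 | 80 × 0.30 = 24 to 80 × 0.50 = 40 | about 19–40 |
| Non-DH | 64 × 0.50 = 32 to 64 × 0.70 = 44.8 | 80 × 0.50 = 40 to 80 × 0.70 = 56 | 32–56 |

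**4. What does pooling buy?** If every subject has a score, the 95% CI half-width in SD units is 1.96 × √(2/n):

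- Overall: n = 64 gives 0.35; n = 80 gives 0.31.
- DH: n = 19.2 gives 0.63; n = 40 gives 0.44.
- Non-DH: n = 32 gives 0.49; n = 56 gives 0.37.

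**5. What could skipping cost?** Protocol Section 2 cites bleaching sensitivity in 10% to 90% of people, across agents and methods. If that range applied here, the subjects with scores at Visit 3 would number between 64 × 0.10 = 6.4 and 80 × 0.90 = 72 per arm. This shows only that the loss is unknown and could be large.

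**The case against.** The strongest reply is that this is one exploratory objective, that the protocol never named a model for these scores, and that the SAP reports n, mean, SD and SE per product within each stratum. From those a reader could compute stratum differences, a combined difference and approximate intervals. The count of sensitive subjects would also make any selection visible. All of that is correct. It limits the point to an unfilled commitment: no specified method was dropped. It does not supply a pre-specified estimate, and intervals rebuilt from sensitive-only means would carry the same selection.

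Several stronger readings are tempting, and the documents do not support them:

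- **That no overall result will exist.** The title of Table 14.2.4.1 does not mention strata and its shell is not in the documents, so a pooled column cannot be ruled out. What can be said is that no SAP text provides for one.
- **That No answers are certainly treated as missing.** Their coding is unstated. The no-imputation rule does not say whether a designed skip counts as missing.
- **That only 64 per arm are available.** That figure belongs to week 24.
- **That the proportion with sensitivity must be formally compared.** The protocol promises only summary statistics for it, and the SAP delivers them.
- **That every scale has a natural no-sensitivity score.** The VAS does. The NRS starts at 1 and measures bother, and the LMS figures are not shown.

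Scoring No responders at one end may also create a spike that fits an ANCOVA poorly. That is a fair caution, and the fix allows for it.

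**Conclusion.** The point stands as a correction that should be made before unblinding. The protocol says the sensitivity scores will be analyzed overall and by stratum. The SAP specifies description within strata, no between-product difference or interval, and no rule for No responders, while recording no departure. The missing estimate and the missing rule are plain from the text. The sensitive-only reading of the means is the likely result of following the SAP, not a stated one.

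On size, a pooled Visit 3 comparison could use roughly 64–80 subjects per arm (half-width about 0.31–0.35 SD), against about 19–40 in the DH stratum (0.44–0.63 SD). This rests on 30–50% DH prevalence, dropout before Visit 3 of at most 20%, and every subject having a score. The direction and amount of any selection bias cannot be quantified from the documents. The success criterion, 24-week VITA shade, is untouched.

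**What to change.** In SAP 4.4.3.1 and Table 14.2.4.1:

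1. Add an overall summary by product alongside the stratum summaries.
2. At Visit 3, give a between-product difference with 95% CI for each score. Overall, adjust for DH stratum and Visit 1 score; also report it within each stratum. Visit 1 is preferable to Visit 2 as covariate because that questionnaire is completed before the first brushing with study product (Protocol 8.1). Visit 2 follows two weeks of use, and adjusting for it could remove part of the effect.
3. State how a No is scored, identically at all three visits. Use the lowest value where the form has such an anchor (for example VAS 0). Where a scale has none, say that its result is conditional on reporting sensitivity.
4. If the spike at the lowest value violates the model assumptions, use the Van Elteren fallback the SAP already applies to its other modelled endpoints.
5. Label the results exploratory and unadjusted for multiplicity.

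If the sponsor wants description only, record that departure in SAP section 5.

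The cost is one extra table and some SAP wording, with no new data. Six scores (VAS, four LMS, NRS) at three levels (overall, DH, non-DH) give 6 × 3 = 18 unadjusted intervals. With no true effect, about 18 × 0.05 = 0.9 would be expected to exclude zero by chance, which is why the labelling matters.

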##### **4.4.3.2 Exploratory Efficacy Variable 2**

The Exploratory Endpoint 2 will be Post Whitening Questionnaire and Whitening History Questionnaire to explore subject's experience of peroxide tooth bleaching when simultaneously using either Test Dentifrice or Reference Dentifrice.

- Whitening History Questionnaire

Individual data from questionnaire will be listed for each subject by study product group in Listing 16.2.6.5 for all randomized subjects.

- Post Whitening Questionnaire

The questionnaire will be summarized [n (%)] for all questions and subject's response in Table 14.2.4.2 for all subjects in the mITT Population by study product group.

Haleon Confidential

CCI

Statistical Analysis Plan Template v7.0

Page 20 of 31

Individual data will be listed for each subject by study product group in Listing 16.2.6.4 for all randomized subjects.

